5.8.1. Adverse Events

Definitions

For safety variables, 2 periods are defined:

- The pretreatment period is defined as the time from signing the ICF to before study drug administration
- The observation period is defined as the time of study drug administration to the last study visit

Treatment-emergent SAEs and AESIs are defined as those that are not present at baseline or represent the exacerbation of a pre-existing condition during the observation period.

Analysis

All SAEs and AESIs reported in this study will be coded using the currently available version of the Medical Dictionary for Regulatory Activities (MedDRA[®]). Coding will be to lowest level terms. The preferred term (PT), and the primary system organ class (SOC) will be listed.

Summaries by treatment group will include the following:

- The number (n) and percentage (%) of patients with at least 1 treatment-emergent serious adverse events (SAEs) through day 29 by system organ class and PT
- The number (n) and percentage (%) of patients with at least 1 infusion-related reactions (grade ≥2), through day 4 by PT
- The number (n) and percentage (%) of patients with at least 1 hypersensitivity reactions (grade ≥2), through day 29 by PT

Summaries of SAEs and AESIs by treatment group will include:

- The number (n) and percentage (%) of patients with at least 1 event by SOC and PT
- SAEs and AESIs by severity (according to the grading scale outlined in Section 4.6.1), presented by SOC and PT
- SAEs and AESIs by relationship to treatment (related, not related), presented by SOC and PT
- Treatment-emergent SAEs and AESIs
- The number (n) and percentage (%) of patients with Grade 3 or Grade 4 treatment-emergent adverse events (cohort 2 and cohort 3 <18 years only).

Deaths and other SAEs will also be listed and summarized by treatment arm.

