3.3.1. Summary of Efficacy and Safety Profile in Clinical Trials

Clinical trial data are summarized below. Overall, REGN10933+REGN10987 have demonstrated efficacy as an anti-viral agent for the treatment and prevention of COVID-19, across a variety of populations, and is generally well-tolerated with an acceptable safety profile.

Clinical Benefit of REGN10933+REGN10987 in Clinical Trials for the Treatment of COVID-19. In COV-2067, the phase 3 outpatient treatment trial, a single intravenous dose of REGN10933+REGN10987 was shown (relative to placebo) to reduce COVID-19-related hospitalizations or all-cause death by 71.3% (2400 mg dose) and 70.4% (1200 mg dose), reduce symptom duration by 4 days (2400 mg and 1200 mg), and reduce viral load over the first 7 days. Serious adverse events occurred more frequently in the placebo group (4.0%) than in either treatment group (2400 mg, 1.1%; 1200 mg, 1.3%), and grade ≥2 infusion-related reactions were infrequent (<0.3% in all groups) (Weinreich, 2021b). Similar virologic efficacy and a similar safety profile were observed in the phase 1/2 portion of this trial, which evaluated REGN10933+REGN10987 at 8000 mg and 2400 mg IV doses (Weinreich, 2021a).

Clinical Benefit of REGN10933+REGN10987 in Clinical Trials for the Prevention of COVID-19. In COV-2069, the phase 3 prevention trial in those at high risk of infection by a household contact, a single subcutaneous dose of REGN10933+REGN10987 (1200 mg) reduced (relative to placebo) symptomatic SARS-CoV-2 infection by 81.4%, and reduced overall SARS-CoV-2 infection by 66.4%. Serious adverse events occurred at similar frequencies in the treatment group (1%) and placebo group (1%). Injection-site reactions were more common in the treatment group (4%) compared to the placebo group (2%), but no injection-site reactions in the study were grade 3 or above. The majority of injection site reactions occurred within one day and resolved within two days (O'Brien, 2021b).

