- Cumulative incidence of patients with ≥1 COVID-19-related medically-attended visit or all-cause death through day 29
- Days of hospitalization due to COVID-19
- Proportion of patients admitted to an intensive care unit due to COVID-19 by day 29
- Proportion of patients requiring supplemental oxygen due to COVID-19 by day 29
- Proportion of patients requiring mechanical ventilation due to COVID-19 by day 29

- Total number of COVID-19-related medically-attended visits through day 29
- Time to all-cause death
- All-cause death by day 29, day 120, and day 169

Virologic

- Time-weighted average change from baseline in viral load (log₁₀ copies/mL) from day 1 to day 7, as measured by RT-qPCR in nasopharyngeal swab samples (patients enrolled prior to protocol amendment 6 only)
- Change from baseline in viral load at each visit, as measured by RT-qPCR in nasopharyngeal swab samples

Safety

- Proportion of patients with treatment-emergent serious adverse events through day 29
- Proportion of patients with infusion-related reactions (grade ≥2) through day 4
- Proportion of patients with hypersensitivity reactions (grade ≥2) through day 29

PK/ADA

- Concentrations of REGN10933 and REGN10987 in serum
- Immunogenicity, as measured by anti-drug antibodies and neutralizing antibodies to REGN10933 and REGN10987

Cohort 2

The secondary endpoints for phase 3 are:

Clinical

- Proportion of patients with ≥1 COVID-19-related hospitalization or all-cause death through day 29
- Proportion of patients with ≥1 COVID-19-related hospitalization or all-cause death from day 4 through day 29
- Proportion of patients with ≥1 COVID-19-related hospitalization, emergency room visit, or all-cause death through day 29
- Proportion of patients with ≥1 COVID-19-related medically-attended visit or all-cause death through day 29
- Proportion of patients with ≥1 COVID-19-related medically-attended visit by type of visit(s) (hospitalization, emergency room, urgent care, and/or physician's office/telemedicine) through day 29
- Proportion of patients with ≥2 COVID-19-related medically-attended visits through day 29
- Cumulative incidence of patients with ≥1 COVID-19-related hospitalization or allcause death through day 29

- Cumulative incidence of patients with ≥1 COVID-19-related hospitalization, emergency room visit, or all-cause death through day 29
- Cumulative incidence of patients with ≥1 COVID-19-related medically-attended visit or all-cause death through day 29

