10.2.2. Serious Adverse Event

An SAE is any untoward medical occurrence that at any dose:

• Results in **death** – includes all deaths, even those that appear to be completely unrelated to study drug (eg, a car accident in which a patient is a passenger).

- Is **life-threatening** in the view of the investigator, the patient is at immediate risk of death at the time of the event. This does not include an adverse event that had occurred in a more severe form, might have caused death.
- Requires in-patient **hospitalization** (admission after discharge) or **prolongation of existing hospitalization**. In-patient hospitalization is defined as a hospital admission (any duration) or an emergency room visit for longer than 24 hours. Prolongation of existing hospitalization is defined as a hospital stay that is longer than was originally anticipated for the event or is prolonged due to the development of a new adverse event as determined by the investigator or treating physician.
- Results in persistent or significant **disability/incapacity** (substantial disruption of one's ability to conduct normal life functions).
- Is a congenital anomaly/birth defect
- Is an **important medical event** Important medical events may not be immediately life-threatening or result in death or hospitalization, but may jeopardize the patient or may require intervention to prevent one of the other serious outcomes listed above (eg, intensive treatment in an emergency room or at home for allergic bronchospasm; blood dyscrasias or convulsions that do not result in hospitalization; or development of drug dependency or drug abuse).

Criteria for reporting SAEs must be followed for these events (refer to Section 10.1.1 Section 10.1.2).

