1.2.2. Secondary Objectives

The secondary objectives of the phase 3 are:

Cohort 1

- To evaluate the impact of REGN10933+REGN10987 on the resolution of self-reported COVID-19 symptoms compared to placebo
- To evaluate the clinical efficacy of REGN10933+REGN10987 compared to placebo using various measures of COVID-19-related medically-attended visits, including COVID-19-related hospitalizations, emergency room visits, or all-cause death
- To describe the virologic effects of REGN10933+REGN10987 compared to placebo

- To evaluate the safety and tolerability of REGN10933+REGN10987 compared to placebo
- To further characterize the concentrations of REGN10933 and REGN10987 in serum over time
- To assess the immunogenicity of REGN10933 and REGN10987

Cohort 2

- To evaluate the clinical efficacy of REGN10933+REGN10987 compared to placebo using various measures of COVID-19-related medically-attended visits, including COVID-19-related hospitalizations or all-cause death
- To describe the virologic effects of REGN10933+REGN10987 compared to placebo
- To assess the immunogenicity of REGN10933 and REGN10987

Cohort 3

- To characterize the concentrations of REGN10933 and REGN10987 in serum over time
- To assess the immunogenicity of REGN10933 and REGN10987

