4.6.2. Adverse Events of Special Interest

Adverse events of special interest (AESI) are AEs (serious or non-serious) of scientific and medical interest specific to this drug program, for which ongoing monitoring and rapid communication by the investigator to the sponsor will be appropriate.

Treatment-emergent adverse events of special interest for this study are grade ≥ 2 hypersensitivity and grade ≥ 2 infusion-related reactions and any treatment-emergent adverse event that led to a medically-attended visit (phase 3 only), regardless of whether the visit is related to COVID-19.

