5.8. Analysis of Safety Data

The analysis of safety data will be performed on the SAF, as defined in Section 3.2.

The safety analysis will be based on the reported SAEs and AESIs and other safety information (clinical laboratory evaluations and vital signs).

Thresholds for Potential Clinically Significant Values (PCSV) in laboratory variables, vital signs and ECG are defined in Section 10.2.

The summary of safety results will be presented for each treatment group for each cohort.

CONFIDENTIAL

Page 34 of 61

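### The overall SAE and AESI rows include COVID-19 outcomes that the drug is expected to reduce, and no planned summary separates them

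*SAP*

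**What the plan says.** For cohort 1 the secondary safety objective (SAP 1.2.2) is "To evaluate the safety and tolerability of REGN10933+REGN10987 compared to placebo". SAP 1.2.1 makes the same comparison a primary objective for cohort 2. The matching endpoint, "Proportion of patients with treatment-emergent serious adverse events through day 29", is a secondary safety endpoint for cohort 1 (Protocol 4.2) and a primary endpoint for cohort 2 (Protocol 4.1).

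Three definitions decide what enters that proportion and the AESI counts:

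- **Admissions and deaths.** Protocol 10.2.2 counts every death as an SAE and states: "In-patient hospitalization is defined as a hospital admission (any duration) or an emergency room visit for longer than 24 hours". There is no exception for COVID-19. Protocol 10.1.1 requires the reason for the admission to be reported as the SAE.
- **AESIs.** SAP 4.6.2 includes "any treatment-emergent adverse event that led to a medically-attended visit (phase 3 only), regardless of whether the visit is related to COVID-19".
- **Scope of collection.** Protocol 10.1.1 records only targeted events. For cohort 1 through day 29 these are in essence SAEs and AESIs.

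On analysis, SAP 5.8 says: "The summary of safety results will be presented for each treatment group for each cohort". SAP 5.8.1 tabulates the number and percentage of "patients with at least 1 treatment-emergent serious adverse events (SAEs) through day 29 by system organ class and PT". It gives grade 2 or higher infusion-related and hypersensitivity reactions their own tables, adds severity tables and "SAEs and AESIs by relationship to treatment (related, not related), presented by SOC and PT", and lists deaths and other SAEs. Protocol 11.4.5.1 matches. Neither section divides events into COVID-19-related and other.

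**The concern.** COVID-19-related hospitalisation or all-cause death through day 29 is the cohort 1 primary efficacy endpoint. The same admissions and deaths are counted as SAEs. If the drug works, the any-SAE row falls for that reason alone, so a lower figure on active treatment does not show whether other serious events rose. The AESI row has the same feature through visit-related events. It also applies to any SOC or preferred term that a drug effect would share with COVID-19 complications, such as respiratory terms.

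This matters more here than in a trial that collects all adverse events, because no general adverse event table exists to fall back on. A reader who wants the proportion of patients with a serious event other than COVID-19 cannot rebuild it from preferred-term rows: one patient may appear in several rows, and the rows do not show which events were COVID-19.

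**Working it through.** **1. Reproduce the plan's figure.** The documents state no safety hypothesis, margin or power. The nearest stated figure using the relevant rates is the efficacy power in Protocol 11.2 and SAP 2.2: about 76% for 3.4% versus 1.7%, with 1248 per group in the mFAS and two-sided alpha 0.05.

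- Formula: power = Φ[(Δ − 1.96·SE₀)/SE₁], with SE₀ = √[2p̄(1−p̄)/n] and SE₁ = √{[p₁(1−p₁)+p₂(1−p₂)]/n}.
- Inputs: Δ = 0.017, p̄ = 0.0255, n = 1248. These give SE₀ = 0.00631 and SE₁ = 0.00630.
- Result: Φ(0.735) = 76.9%, in line with the stated figure.

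**2. Size of the possible offset.** If those rates carried over to the any-SAE row, efficacy would lower the active arm by 3.4% − 1.7% = 1.7 points. Then 0.017 × 1248 = 21.2, so drug-caused SAEs in about 21 patients per 1248 would leave the any-SAE row level.

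**3. What a separate row would show.** This step needs a background rate of non-COVID SAEs, which the documents do not give. I assume 1% (range 0.3% to 2%), and that COVID-19 and other SAEs fall in different patients. The visibility columns give the chance of a nominal two-sided 0.05 difference against the drug at 1248 per arm, by the formula in step 1 with the sign of Δ set for harm. They only express how visible an excess would be, since the plan tests nothing here.

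| Drug-caused excess | Any-SAE row, placebo vs active | Visibility | Non-COVID row, placebo vs active | Visibility (background 2% to 0.3%) |
|---|---|---|---|---|
| 1.0 point | 4.4% vs 3.7% | 0.2% | 1.0% vs 2.0% | 54% (36% to 80%) |
| 1.7 points | 4.4% vs 4.4% | 2.5% (chance level) | 1.0% vs 2.7% | 88% (72% to 98%) |

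For example, the 1.7-point case gives a placebo rate of 3.4 + 1.0 = 4.4% and an active rate of 1.7 + 1.0 + 1.7 = 4.4%.

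**4. Reported totals.** Protocol 3.3.1 gives SAEs in 4.0% on placebo, 1.1% on 2400 mg and 1.3% on 1200 mg. The differences are 4.0 − 1.1 = 2.9 and 4.0 − 1.3 = 2.7 points. The overall row therefore does run in the drug's favour, but the protocol does not say how many of these SAEs were COVID-19.

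I give no figure for AESIs. The documents give no phase 3 rate for visit-related adverse events, and a COVID-19 visit becomes an AESI only if a treatment-emergent adverse event led to it.

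**The case against.** The case on the other side is substantial.

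- **Safety is not tested.** The phase 3 hypotheses and the testing hierarchy (SAP 5.7.1 and 5.7.3) concern efficacy only. A reader might infer from the comparative objective that a safety conclusion hangs on a test of the SAE total. The documents attach no p-value, margin or alpha to it.
- **The plan is not limited to totals.** A reader might infer that a drug effect could vanish altogether. It could not if it has its own term: it would appear in its SOC/PT row and in the SAE listing whatever the efficacy. Infusion-related and hypersensitivity reactions already have separate tables. What remains exposed is the overall rows, the shared terms, and an excess spread thinly over many terms.
- **Attribution is a judgement either way.** The relatedness tables rest on the investigator, and so would a COVID-19 split. An event wrongly called COVID-19 would drop out of the non-COVID row.
- **A non-COVID table can hide a named harm.** Protocol 3.3.2 discusses antibody-dependent enhancement, which could worsen the disease. Such events would be classed as COVID-19. The non-COVID row therefore must not replace the all-SAE table as the basis of the comparison.
- **Other safeguards exist.** The IDMC reviews all efficacy and safety data, including deaths (Protocol 6.2.1), and fuller adverse event collection was assigned to the prophylaxis and volunteer studies (Protocol 3.2.1.3). Both help, but neither puts the missing split into this trial's tables.

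These points limit the concern and shape the fix. They do not supply the separation.

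**Conclusion.** The point holds as a cheap improvement to the safety tables. The any-event SAE and AESI rows partly re-measure efficacy, and no planned summary separates the COVID-19 component. In those rows and in shared terms, an excess of other serious events could be offset by about 1.7 points on the plan's own rates.

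That size is illustrative. The 3.4% and 1.7% are mFAS planning rates that include all-cause death, while the safety analysis uses the SAF, meaning all treated patients analysed as treated. The non-COVID background in the table is my assumption.

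The point applies to cohorts 1 and 2 for patients randomised while placebo was in use. It does not apply to cohort 3, which has no placebo arm.

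A reader might go further and infer that the reported 4.0% versus 1.1% and 1.3% conceals harm, or that the safety objective goes unanswered. The documents support neither: they do not break those SAEs down by cause, and the SOC/PT, severity, relatedness and reaction tables, with the listings, answer part of the question.

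**What to change.** In SAP 5.8.1 and Protocol 11.4.5.1, keep the all-SAE table as planned and add beside it, by treatment group:

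1. The number and percentage of patients with at least one treatment-emergent SAE through day 29 that is not a COVID-19-related hospitalisation or a COVID-19 death.
2. Treatment-emergent adverse events that led to a medically-attended visit, split into COVID-19-related and not. The other two AESI components already have their own tables.

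State the classification rule. Link SAE records to the investigator-determined COVID-19 visit record (Protocol 9.2.3.2), and classify deaths by the reported cause-of-death SAE term. The rule has to be written down because the COVID-19 determination is described for visits, not for SAE records or deaths.

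Say that the two SAE tables are to be read together, since attribution is investigator-judged and drug-caused worsening of COVID-19 would appear only in the all-SAE and COVID-19 rows. Label the cohort 1 tables as added after the primary results were reported, because Protocol 3.3.1 already gives those results.

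The cost is the wording, the linking rule and two tables. No new data collection is needed.

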5.8.2. Clinical Laboratory Measurements

Laboratory measurements include clinical chemistry and hematology results, and will be converted to standard international units and US conventional units. Summaries of laboratory variables based on standard international units will include:

- Descriptive statistics of laboratory result and change from baseline to Day 29. Summary statistics will include the number of patients, mean, median, standard deviation, quartiles, minimum, and maximum.
- Number and percentage of patients with a potentially clinically significant value (PCSV) at any post-randomization time point will be summarized for each clinical laboratory test for all patients and separately for patients in whom the PCSV criterion was normal or missing at baseline.
- Shift tables based on baseline normal/abnormal and other tabular and graphical methods may be used to present the results for parameters of interest.

Listing of all laboratory parameters normal range and abnormal flag by patient and visit will be provided.

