9.2.10.2. Serum and Plasma Biomarkers

Changes in circulating concentrations of serum/plasma biomarkers associated with inflammation, coagulation, and disease progression will be assessed in REGN10933+REGN10987 group compared to the placebo group in phase 1 and phase 2. The association between changes in disease related biomarkers with clinical endpoints may be evaluated.

Biomarkers may include (but are not limited to) CRP, LDH, D-dimer, and ferritin. CRP is a general inflammation marker that correlates with severity of COVID-19 including lung lesions, supplemental O₂ requirements, and death (Luo, 2020) (Qin, 2020). LDH was identified as a predictive factor for early recognition of lung injury and advanced COVID-19 cases (Ruan, 2020) (Wang, 2020b) (Young, 2020). Ferritin is a general inflammation marker associated with severity

of COVID-19 (Qin, 2020). D-dimer levels >1 μ g/mL have been reported to identify patients with poor prognosis for COVID-19 (Zhou, 2020).

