11.4.5.2. Other Safety

Vital Signs

Vital signs (temperature, pulse, blood pressure, and respiration rate) will be summarized by baseline and change from baseline to each scheduled assessment time with descriptive statistics.

Laboratory Tests

Laboratory test results will be summarized by baseline and change from baseline to each scheduled assessment time with descriptive statistics.

Number and percentage of patients with a potentially clinically significant value (PCSV) at any post-randomization time point will be summarized for each clinical laboratory test for all patients and separately for patients in whom the PCSV criterion was normal or missing at baseline.

Shift tables based on baseline normal/abnormal and other tabular and graphical methods may be used to present the results for laboratory tests of interest.

Listings will be provided with flags indicating the out of laboratory range values.

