- 15. In **cohort 2 (and patients <18 years in cohort 3)**, each patient will be assigned at randomization by IWRS to a blood sample collection schedule for drug concentration and immunogenicity analysis. Actual dosing time and PK-ADA sample collection times will be recorded. To conserve blood volume, a single blood draw for drug concentration and immunogenicity will be obtained.
- 16. Patients will be followed by phone at day 120 and day 169 for vital status, pregnancy status, targeted safety information, and additional safety information in newborns of study participants. Refer to Section 9.2.5 for more information on these follow-up assessments.
- 17. For patients <12 years in cohort 2 and cohort 3, follow-up by phone will be conducted within 6 to 8 hours of infusion to collect the information indicated.

Parameter	PCSV	Comments
Clinical Chemis	try	
ALT*	>3 and \leq 5 ULN and baseline \leq 3 ULN*	Enzymes activities must be expressed in ULN, not in IU/L.
	>5 and ≤ 10 ULN and baseline ≤ 5 ULN	Concept paper on DILI – FDA draft Guidance Oct 2007.
	>10 and ≤ 20 ULN and baseline ≤ 10 ULN	Each category is calculated independently.
	>20 ULN and baseline ≤ 20 ULN	* At least one level is required; multiple levels are optional for phase 2/3 studies. If it is desirable to get the distribution across the different PCSV levels, additional shift table on $\leq 3, >3$ to $\leq 5, > 5$ to $\leq 10, >10$ to ≤ 20 , and > 20 category for baseline vs. post baseline may be provided
AST*	 >3 and ≤ 5 ULN and baseline ≤ 3 ULN* >5 and ≤ 10 ULN and baseline ≤ 5 ULN >10 and ≤ 20 ULN and baseline ≤ 10 ULN 	Enzymes activities must be expressed in ULN, not in IU/L. Concept paper on DILI – FDA draft Guidance Oct 2007. Each category is calculated independently.
	>20 ULN and baseline ≤ 20 ULN	* At least one level is required, multiple levels are optional for phase 2/3 studies. If it is desirable to get the distribution across the different PCSV levels, additional shift table on $\leq 3, >3$ to $\leq 5, > 5$ to $\leq 10, >10$ to ≤ 20 , and > 20 category for baseline vs. post baseline may be provided
Alkaline Phosphatase	>1.5 ULN and baseline \leq 1.5 ULN	Enzyme activity must be expressed in ULN, not in IU/L. Concept paper on DILI – FDA draft Guidance Oct 2007.

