Blood Urea Nitrogen	≥17 mmol/L or ≥ULN (if ULN≥17 mmol/L) and baseline <17 mmol/L or <uln (if="" l)<="" mmol="" td="" uln≥17="">Two independent criteria	</uln>	Two independent criteria
Chloride		Two independent criteria
Hypochloremia:	<80 mmol/L or <lln (if="" and="" baseline
≥ 80 mmol/L or ≥LLN (if LLN≤80 mmol/L)</lln>	
	>115 mmol/L or >ULN (if ULN≥115 mmol/L) and baseline ≤ 115 mmol/L or ≤ULN (if ULN≥115 mmol/L)	
Hyperchloremia:		
Sodium		Two independent criteria
Hyponatremia:	≤129 mmol/L or ≤LLN (if LLN≤129 mmol/L) and baseline > 129 mmol/L or >LLN (if LLN≤129 mmol/L)	
	≥160 mmol/L or ≥ULN (if ULN≥160 mmol/L) and baseline <160 mmol/L or <uln (if="" l)<="" mmol="" td="" uln≥160="">	</uln>	
Hypernatremia:		

Regeneron Pharmaceuticals, Inc.

CONFIDENTIAL

Parameter	PCSV	Comments
Potassium		FDA Feb 2005.
Hypokalemia	<3 mmol/L or <lln (if="" lln<math="">\leq3 mmol/L) and baseline \geq 3 mmol/L or \geqLLN (if LLN\leq3 mmol/L)</lln>	Two independent criteria
	≥5.5 mmol/L or ≥ULN (if ULN≥5.5 mmol/L) and baseline <5.5 mmol/L or <uln (if="" l)<="" mmol="" td="" uln≥5.5="">	</uln>	
Hyperkalemia		
Total Cholesterol	≥7.74 mmol/L or ≥ULN (if ULN≥7.74 mmol/L) and baseline < 7.74 mmol/L or <uln (if="" l)<="" mmol="" td="" uln≥7.74="">Threshold for therapeutic intervention.	</uln>	Threshold for therapeutic intervention.
Triglycerides	≥4.6 mmol/L or ≥ULN (if ULN≥4.6 mmol/L) and baseline < 4.6 mmol/L or <uln (if="" l)<="" mmol="" td="" uln≥4.6="">Threshold for therapeutic intervention.	</uln>	Threshold for therapeutic intervention.
Lipasemia	\geq 3 ULN and baseline < 3 ULN	
Amylasemia	\geq 3 ULN and baseline < 3 ULN	
Glucose		
	\leq 3.9 mmol/L and \leq LLN and baseline $>$ 3.9 mmol/L or \geq LLN	ADA Jan 2008.
Hypoglycaemia	≥11.1 mmol/L (unfasted); ≥7 mmol/L (fasted) and baseline < 11.1 mmol/L (unfasted); <7 mmol/L (fasted)	
Hyperglycaemia		
HbA1c	$>8\%$ and baseline $\leq 8\%$	
Albumin	\leq 25 g/L or \leq LLN (if LLN \leq 25 g/L) and baseline >25 g/L or >LLN (if LLN \leq 25 g/L)	
CRP	>2 ULN or >10 mg/L (if ULN not provided) and baseline ≤2 ULN or ≤10 mg/L (if ULN not provided)	FDA Sept 2005.

Parameter	PCSV	Comments
Hematology		

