WBC	<3.0 Giga/L or <lln (if="" and="" baseline="" giga="" l)="" lln≤3.0="" ≥3.0
Giga/L or ≥LLN (if LLN≤3.0 Giga/L) (Non-Black); <2.0 Giga/L or <lln (if="" and="" baseline="" giga="" l)="" lln≤2.0="" ≥2.0
Giga/L or ≥LLN (if LLN≤2.0 Giga/L) (Black)*</lln></lln>	Increase in WBC: not relevant. *The default criteria. Summary by race (black and Non- black) are optional. To be interpreted only if no differential count available.
	≥16.0 Giga/L or ≥ULN (if ULN≥16.0 Giga/L) and baseline < 16 Giga/L or <uln (if="" giga="" l)<="" td="" uln≥16.0="">	</uln>	
Lymphocytes	>4.0 Giga/L or >ULN (if ULN \geq 4.0 Giga/L) and baseline \leq 4.0 Giga/L or \leq ULN (if ULN \geq 4.0 Giga/L)	
Neutrophils	<1.5 Giga/L or <lln (if="" for="" giga="" l)="" lln≤1.5="" non-black="" or
<1.0 Giga/L or <lln (if="" and="" baseline
≥1.5 Giga/L or ≥LLN (if LLN≤1.5 Giga/L) for Non-Black or ≥1.0 Giga/L or ≥LLN (if LLN≤1.0 Giga/L) for Black*</lln></lln>	International Consensus meeting on drug-induced blood cytopenias, 1991. *The default criteria. By race (black and Non-black) are optional.
	<1.5 Giga/L or <lln (if="" and="" baseline="" giga="" l)="" lln≤1.5="" ≥1.5
Giga/L or ≥LLN (if LLN≤1.5 Giga/L) (Non-Black); <1.0 Giga/L or <lln (if="" and="" baseline="" giga="" l)="" lln≤1.0="" ≥1.0
Giga/L or ≥LLN (if LLN≤1.0 Giga/L) (Black)</lln></lln>	
	<0.5 Giga/L regardless of baseline value or racce	
Monocytes	>0.7 Giga/L or >ULN (if ULN≥0.7 Giga/L) and baseline ≤ 0.7 Giga/L or ≤ULN (if ULN≥0.7 Giga/L)	
Basophils	>0.1 Giga/L or >ULN (if ULN \geq 0.1 Giga/L) and baseline \leq 0.1 Giga/L or \leq ULN (if ULN \geq 0.1 Giga/L)	
Eosinophils	>0.5 Giga/L or >ULN (if ULN≥0.5 Giga/L) and baseline ≤0.5 Giga/L or ≤ULN (if ULN≥0.5 Giga/L)	Harrison- Principles of Internal Medicine 17 th Ed., 2008.

Regeneron Pharmaceuticals, Inc.

CONFIDENTIAL

Parameter	PCSV	Comments
Hemoglobin	\leq 115 g/L or \leq LLN (if LLN \leq 115 g/L) for male or \leq 95 g/L or \leq LLN (if LLN \leq 95 g/L) for female and baseline > 115 g/L or	Three criteria are independent.
	>LLN (if LLN≤115 g/L) for male or >95 g/L or >LLN (if LLN≤95 g/L) for Female*	*The default criteria. By gender (male and female) are optional.
	\leq 115 g/L or \leq LLN (if LLN \leq 115 g/L) and baseline > 115 g/L or >LLN (if LLN \leq 115 g/L) for male;	Criteria based upon decrease from baseline are more relevant than based on absolute value. Other categories for

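### Most laboratory PCSV criteria in SAP Appendix 10.2 already contain a baseline condition, so the all-patients count in SAP 5.8.2 adds no events to the subset count

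*SAP*

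**What the plan says.** For each laboratory test, SAP 5.8.2 plans the number and percentage of patients with a PCSV at any time after randomization, "for all patients and separately for patients in whom the PCSV criterion was normal or missing at baseline". Protocol 11.4.5.2 plans the same two summaries: "for each clinical laboratory test for all patients and separately for patients in whom the PCSV criterion was normal or missing at baseline".

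The criteria are in an appendix. SAP 5.8 states: "Thresholds for Potential Clinically Significant Values (PCSV) in laboratory variables, vital signs and ECG are defined in Section 10.2". Three rows of that appendix show the pattern:

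- CRP, a single threshold with a baseline clause: ">2 ULN or >10 mg/L (if ULN not provided) and baseline ≤2 ULN or ≤10 mg/L (if ULN not provided".
- ALT, one of several tiers: ">5 and ≤ 10 ULN and baseline ≤ 5 ULN". The comment beside it reads "At least one level is required; multiple levels are optional for phase 2/3 studies".
- Neutrophils, lowest level: "<0.5 Giga/L regardless of baseline value or racce".

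SAP 5.8.2 also requires change-from-baseline statistics and a by-patient, by-visit listing with abnormality flags. Shift tables are optional. SAP 6.3 has no rule for a missing laboratory baseline.

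**The concern.** Two summaries are useful only if they can differ in the events they count. The all-patients summary should show everyone who reached a notable value after dosing. The subset summary should show those in whom it was new, or could not be shown to be old. If the criterion itself excludes patients already past the threshold, the first summary loses its purpose, and the second loses the missing-baseline patients it is meant to hold.

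Baselines past a threshold are foreseeable here. Protocol 7.2.1 admits patients through chronic kidney disease (including dialysis), chronic liver disease and immunosuppression, and all have acute COVID-19. Protocol 9.2.10.2 notes that "CRP is a general inflammation marker that correlates with severity of COVID-19", so CRP may well be raised at entry.

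Adverse event collection is also restricted. Under Protocol 10.1.1 only targeted events are recorded, and grade 3 and 4 events as such are collected in phase 3 only for patients under 18. In an adult, a laboratory deterioration that is not serious, led to no medical visit and is not a reaction to the drug may appear only in the laboratory outputs.

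**Working it through.** The plan states no figure for this point, so the check is to classify the criteria and apply them literally.

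**Step 1. Classify the laboratory criteria.** We counted the default rows of Appendix 10.2 and did not count the optional repeats by race or sex a second time.

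| Group | With baseline threshold clause | Without | Total |
|---|---|---|---|
| Chemistry | 38 | 2 | 40 |
| Hematology | 14 | 2 | 16 |
| Urine pH | 2 | 0 | 2 |
| All | 54 | 4 | 58 |

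The share with a clause is 54/58 = 93.1%. The four without are creatinine change of at least 30% and of at least 100%, a hemoglobin fall of at least 20 g/L, and neutrophils below 0.5 Giga/L.

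The appendix also lists tests that Protocol 9.2.7 does not. Removing conjugated bilirubin (1), uric acid (2), cholesterol (1), triglycerides (1), lipase (1), amylase (1), HbA1c (1) and urine pH (2) takes away 10 criteria, all with a clause. That leaves 44 of 48, or 91.7%.

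**Step 2. Compare the two numerators.** Take the subset to be patients whose baseline value did not pass the threshold in question, or was missing. For any of the 54 criteria, a patient who meets it has a recorded baseline short of the threshold and is therefore in the subset. Both counts then have the same numerator x. Let N be all patients and f the share already past the threshold at baseline, so that the subset has N(1 − f) patients. Then

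x/N = (1 − f) × x/[N(1 − f)].

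The all-patients percentage is the subset percentage times (1 − f). It carries no information on what happened after dosing to patients already past the threshold.

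**Step 3. Missing baseline.** A missing value cannot satisfy a clause on the baseline. The three change-from-baseline criteria also need a baseline value. So 54 + 3 = 57 of the 58 criteria cannot be met by such a patient; only neutrophils below 0.5 Giga/L can.

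**Step 4. Tiered tests.** Of the 54, 11 are higher tiers that a patient past a milder limit can still meet: ALT 3, AST 3, creatinine clearance 3, total bilirubin 1, CPK 1. For ALT in multiples of ULN:

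| Baseline | After dosing | As written | Threshold alone |
|---|---|---|---|
| 1 | 4 | counted | counted |
| 4 | 4.8 | not counted | counted |
| 4 | 6 | counted if higher tiers are used | counted |
| 6 | 12 | counted if higher tiers are used | counted |
| missing | 6 | not counted | counted |

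Only one level is mandatory for ALT, AST, total bilirubin and CPK, and creatinine clearance is optional altogether. Single-threshold tests have no such second chance.

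**The case against.** **The appendix may be meant only to supply thresholds.** SAP 5.8 says that it defines thresholds, while 5.8.2 defines the patient groups and places missing baselines with normal ones. A programmer could let 5.8.2 govern. That is a fair reading, and the SAP does not say which text prevails. But the neutrophil row, which expressly sets baseline aside, implies that the clause is operative elsewhere. Two programmers could produce different tables.

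**Other outputs show the same data.** Change-from-baseline summaries and the flagged listing are mandatory, and Protocol 9.2.7 requires significantly abnormal results to be repeated. This is a real mitigation. However, means can hide individual extremes, and a listing gives no rate by arm.

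**Clinical worsening is captured elsewhere.** The primary endpoint, serious events and events leading to a medical visit all do this, and Protocol 3.3.2 treats antibody-dependent enhancement as theoretical. The CRP remark comes from an exploratory biomarker section whose treatment comparison is described for phases 1 and 2. This limits the stakes.

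**A reader might infer more than the documents support.**

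- *That a normal baseline is required.* The clause usually asks only that the baseline has not passed the PCSV threshold. A patient with ALT at 2 ULN remains eligible.
- *That worsening from an abnormal baseline is never counted.* The four criteria without a baseline threshold and, where used, the 11 higher tiers can count it. Chronic kidney and liver disease are partly covered by the creatinine changes and by the ALT, AST and bilirubin tiers.
- *That the all-patients rate is understated by some stated fraction.* The documents give no baseline laboratory distribution, so any figure would come from assumed inputs. It would also mix persisting abnormalities with worsening.

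**Conclusion.** The concern holds as an internal conflict between SAP 5.8.2 (with Protocol 11.4.5.2) and Appendix 10.2. Read literally, the two summaries have one numerator for 54 of 58 laboratory criteria, or 44 of 48 among tests listed in Protocol 9.2.7. Missing-baseline patients cannot be counted under those criteria. For single-threshold tests, further worsening in a patient already past the threshold goes uncounted.

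This rests on applying Appendix 10.2 as written and on taking a normal criterion at baseline to mean one whose threshold was not passed. No numerical understatement can be derived from the documents. The outputs are descriptive and the same rule applies to every arm; alpha, power and the efficacy analyses are untouched. It is worth correcting because the SAP would otherwise not deliver a table that both documents promise.

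**What to change.** 1. In Appendix 10.2, put the post-baseline threshold and the baseline clause in separate columns. The threshold values themselves are not in question.
2. For the all-patients count, apply the post-baseline threshold alone.
3. For the subset count, apply the baseline clause, and treat a missing baseline as not past the threshold, as 5.8.2 provides. State that change-from-baseline criteria cannot be evaluated without a baseline.
4. For single-threshold tests, commit to a shift table of baseline against worst post-baseline value, which 5.8.2 already permits.

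The cost is SAP wording and programming on data already collected. The downside is that the all-patients count will include stable pre-existing abnormalities; the subset count and the shift table separate these out.
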